**Table JAIN.6.12. Description of Health Outcomes and Quality-of-Life Measures Analyses (Period 3 and Period 4)**

Measure	Variable	Population (Section 6.2.1)	Analysis Method (Section 6.2.2)	Time Point	Baseline Definition
Itch Numeric Rating Scale (NRS)	Itch NRS score	LTE Substudy Population	Descriptive using Obs and mLOCF	Weeks 52-68	Week 52 Baseline
	Change from baseline in Itch NRS score	LTE Substudy Population - Patients with IGA of 0 or 1 at Week 52	Descriptive using Obs and mLOCF	Weeks 52-68	Week 52 Baseline
	Percent change from baseline in Itch NRS score	LTE Non-responder Population	Descriptive using Obs and mLOCF	Weeks 52-68	Week 52 Baseline
		LTE Responders & Partial Responders who did not enter the study	Descriptive using Obs and mLOCF	Weeks 52-68	Week 0 Baseline
	Proportion of patients with a 4-point improvement from baseline of originating study in Itch NRS in subgroup of patients who had baseline Itch NRS $\geq 4$	LTE Substudy Population	Descriptive using Obs and mLOCF	Weeks 52-68	Week 0 Baseline
		LTE Substudy Population – Patients with IGA of 0 or 1 at Week 52	Descriptive using Obs and mLOCF	Weeks 52-68	Week 0 Baseline
		LTE Non-responder Population	Descriptive using Obs and mLOCF	Weeks 52-68	Week 0 Baseline
		LTE Responders & Partial Responders who did not enter the study	Descriptive using Obs and mLOCF	Weeks 52-68	Week 0 Baseline
	Skin Pain NRS	LTE Substudy Population	Descriptive using Obs and mLOCF	Weeks 52-68	Week 52 Baseline
	Change from baseline in Skin Pain NRS score				

Measure	Variable	Population (Section 6.2.1)	Analysis Method (Section 6.2.2)	Time Point	Baseline Definition
Skin Pain NRS	Skin Pain NRS score Change from baseline in Skin Pain NRS score	LTE Substudy Population with Week 52 IGA of 0 or 1	Descriptive using Obs and mLOCF	Weeks 52-68	Week 52 Baseline
		LTE Non-responder Population	Descriptive using Obs and mLOCF	Weeks 52-68	Week 52 Baseline
	Proportion of patients with a 4-point improvement from baseline of originating study in Skin Pain in subgroup of patients who had baseline Skin Pain NRS $\geq 4$	LTE Responders & Partial Responders who did not enter the study	Descriptive using Obs and mLOCF	Weeks 52-68	Week 0 Baseline
		LTE Substudy Population	Descriptive using Obs and mLOCF	Weeks 52-68	Week 0 Baseline
		LTE Substudy Population - Patients with IGA of 0 or 1 at Week 52	Descriptive using Obs and mLOCF	Weeks 52-68	Week 0 Baseline
		LTE Non-responder Population	Descriptive using Obs and mLOCF	Weeks 52-68	Week 0 Baseline
		LTE Responders & Partial Responders who did not enter the study	Descriptive using Obs and mLOCF	Weeks 52-68	Week 0 Baseline
Atopic Dermatitis Sleep Scale (ADSS)	ADSS item (1, 2, 3) scores	LTE Substudy Population	Descriptive using Obs and mLOCF	Weeks 52-68	Week 52 Baseline
		LTE Substudy Population – Patients with IGA of 0 or 1 at Week 52	Descriptive using Obs and mLOCF	Weeks 52-68	Week 52 Baseline
	Change from baseline in ADSS item scores	LTE Non-responder Population	Descriptive using Obs and mLOCF	Weeks 52-68	Week 52 Baseline
		LTE Responders & Partial Responders who did not enter the study	Descriptive using Obs and mLOCF	Weeks 52-68	Week 0 Baseline
Atopic Dermatitis Sleep Scale (ADSS)		LTE Substudy Population	Descriptive using Obs and mLOCF	Weeks 52-68	Week 0 Baseline
		LTE Substudy Population – Patients with IGA of 0 or 1 at Week 52	Descriptive using Obs and mLOCF	Weeks 52-68	Week 0 Baseline
		LTE Non-responder Population	Descriptive using Obs and mLOCF	Weeks 52-68	Week 0 Baseline

	Proportion of patients with a 1.5-point improvement from baseline of originating study in Item 2 score of ADSS, in a subgroup of patients with baseline Item 2 score of $\geq 1.5$	LTE Responders & Partial Responders who did not enter the study	Descriptive using Obs and mLOCF	Weeks 52-68	Week 0 Baseline
Patient Global Impression of Severity—Atopic Dermatitis (PGI-S-AD)	PGI-S-AD score	LTE Substudy Population	Descriptive using Obs and mLOCF	Weeks 52-68	Week 52 Baseline
	Change from baseline in PGI-S-AD score	LTE Substudy Population - Patients with IGA of 0 or 1 at Week 52	Descriptive using Obs and mLOCF	Weeks 52-68	Week 52 Baseline
		LTE Non-responder Population	Descriptive using Obs and mLOCF	Weeks 52-68	Week 52 Baseline
		LTE Responders & Partial Responders who did not enter the study	Descriptive using Obs and mLOCF	Weeks 52-68	Week 0 Baseline
Measure	Variable	Population (Section 6.2.1)	Analysis Method (Section 6.2.2)	Time Point	Baseline Definition
Dermatology Life Quality Index (DLQI)	DLQI total score change from baseline in domain and total scores	LTE Substudy Population	Descriptive using Obs and mLOCF	Weeks 52-200	Week 52 Baseline
		LTE Substudy Population – Patients with IGA of 0 or 1 at Week 52	Descriptive using Obs and mLOCF	Weeks 52-200	Week 52 Baseline
		LTE Non-responder Population	Descriptive using Obs and mLOCF	Weeks 52-200	Week 52 Baseline
		LTE Responders & Partial Responders who did not enter the Substudy	Descriptive using Obs and mLOCF	Weeks 52-200	Week 0 Baseline
	Proportion of patients with DLQI (0, 1)	LTE Substudy Population	Descriptive using Obs and mLOCF	Weeks 52-200	DLQI (0,1) N.A. DLQI $\leq 5$ uses Week 0 Baseline
	Proportion of patients with DLQI Total Score	LTE Substudy Population - Patients with IGA of 0 or 1 at Week 52	Descriptive using Obs and mLOCF	Weeks 52-200	DLQI (0,1) N.A. DLQI $\leq 5$ uses Week 0 Baseline

	5 or less with baseline >=4	LTE Non-responder Population	Descriptive using Obs and mLOCF	Weeks 52-200	DLQI (0,1) N.A. DLQI <=5 uses Week 0 Baseline
		LTE Responders & Partial Responders who did not enter the Substudy	Descriptive using Obs and mLOCF	Weeks 52-200	DLQI (0,1) N.A. DLQI <=5 uses Week 0 Baseline

Abbreviations: ADSS = Atopic Dermatitis Sleep Scale; DLQI = Dermatology Life Quality Index; IGA = Investigator's Global Assessment for AD; LTE = Long-Term Extension; ; mLOCF = modified last observation carried forward; NRS = Numeric Rating Scale; Obs = Observed; PGI-S-AD = Patient Global Impression of Severity-Atopic Dermatitis.

Notes: missing data related to COVID-19 may be imputed using the method specified in Section [6.3.7](#).

## 6.12. Bioanalytical and Pharmacokinetic/Pharmacodynamic Methods

Pharmacokinetic, Pharmacodynamic and Biomarker analyses to address secondary and exploratory objectives of this study will be described by Lilly in separate Pharmacokinetic/Pharmacodynamic and Biomarker analysis plans.

## 6.13. Safety Analyses

The general methods used to summarize safety data, including the definition of baseline value are described in Section 6.2.2.

Safety analyses will include all data including rescue to any of the 3 rescue therapy options, unless otherwise stated, and patients will be analyzed according to the investigational product to which they were randomized at Week 0 (Visit 2). For 24-week and 52-week interim lock, safety analyses will use the safety population defined in Section 6.2.1.

For the 24-week and 52-week interim lock, safety topics that will be addressed include the following: AEs, clinical laboratory evaluations, vital signs and physical characteristics, Columbia Suicide Severity Rating Scale (C-SSRS), the Self-Harm Supplement Form, safety in special groups and circumstances, including adverse events of special interest (AESI) (see Section 6.13.4), and investigational product interruptions.

Unless otherwise specified, by-visit summaries will include planned on-treatment visits. For tables that summarize events (such as AEs, categorical laboratory abnormalities, shift to maximum severity), post-last dose follow-up data will be included. Follow-up data is defined as all data occurring up to 30 days (planned maximum follow-up time) after last dose of treatment including rescue, regardless of study period. All safety data from continuing patients at time of the 52-week interim lock will be included in the safety analysis up to the first dose date of period 3. Safety data from patients who permanently discontinued study drug prior to an interim lock will be included in the interim lock safety analysis up to 30 days post last dose.

For the 104-week interim analysis safety topics will be addressed including the following: AEs and AESI (i.e., infections, MACE, VTE, Malignancies).

For the final analyses, safety analyses will use the safety population and Extended Safety analysis will be performed by treatment based on the initial randomization at week 0 including the All BARI group, who received at least one dose of BARI during the study, to address both the safety topics including AEs and AESI (i.e., infections, MACE, VTE, Malignancies). The Compound level safety standards provide further details and information.

Duration of exposure (in days) will be calculated as follows:

- Duration of exposure to investigational product (including exposure after the initiation of rescue therapy): *date of last dose of study drug including rescue – date of first dose of study drug + 1*

Duration of exposure (in days) for the “PBO/BARI 1-mg to BARI 2-mg” and the “PBO/BARI 1-mg/BARI 2-mg to BARI 4-mg” groups will be calculated as follows:

- Duration of exposure to investigational product (including exposure after the initiation of rescue therapy): *date of last dose of study drug including rescue – date of first dose of study drug after the switch + 1*

Last dose of study drug including rescue is calculated as last date on study drug. See the Compound level safety standards for more details.

Total patient-years (PY) of exposure will be reported for each treatment group for overall duration of exposure. Descriptive statistics will be provided for patient-days of exposure, and the frequency of patients falling into different exposure ranges in addition to cumulative exposures will be summarized.

Exposure ranges will be reported in weeks using the following:

- ≥4 weeks, ≥8 weeks, ≥12 weeks, ≥16 weeks, ≥24 weeks, ≥52 weeks, ≥76 weeks, ≥104 weeks, ≥120 weeks, ≥136 weeks, ≥152 weeks, ≥168 weeks, ≥184 weeks and ≥200 Weeks
- >0 to <4 weeks, ≥4 weeks to <8 weeks, ≥8 weeks to <12 weeks, ≥12 to <16 weeks, ≥16 to 24 weeks, ≥24 to 52 weeks, ≥52 to 76 weeks, ≥76 to 104 weeks, and ≥104 to 120 weeks, ≥120 to 136 weeks, ≥136 to 152 weeks, ≥152 to 168 weeks, ≥168 to 184 weeks, ≥184 to 200 weeks, ≥200 Weeks

The exposure ranges for the interim lock(s) will be adjusted accordingly.

**For Week-104 interim analysis**, exposure ranges will be reported in weeks using the following:

- ≥52 weeks, ≥60 weeks, ≥68 weeks, ≥76 weeks, ≥92 weeks, and ≥104 weeks
- ≥52 weeks to <60 weeks, ≥60 weeks to <68 weeks, ≥68 to <76 weeks, ≥76 to 92 weeks, ≥92 to 104 weeks, and ≥104 weeks

**For final analysis**, exposure ranges will be reported in weeks using the following:

- ≥52 weeks, ≥60 weeks, ≥68 weeks, ≥76 weeks, ≥92 weeks, ≥104 weeks, ≥120 weeks, ≥136 weeks, ≥152 weeks, ≥168 weeks, ≥184 weeks, ≥200 weeks
- ≥52 weeks to <60 weeks, ≥60 weeks to <68 weeks, ≥68 to <76 weeks, ≥76 to 92 weeks, ≥92 to 104 weeks, and ≥104 to 120 weeks, ≥120 to 136 weeks, ≥136 to 152 weeks, ≥152 to 168 weeks, ≥168 to 184 weeks, ≥184 to 200 weeks, ≥200 Weeks

Overall exposure will be summarized in total PY, which is calculated according to the following formula:

*Exposure in PY (PYE) = sum of duration of exposure in days (for all patients in treatment group) / 365.25*

### 6.13.1. Adverse Events

Adverse events are recorded in the eCRFs. Each AE will be coded to System Organ Class (SOC) and Preferred Term (PT) using the Medical Dictionary for Regulatory Activities

(MedDRA) version that is current at the time of DBL. Severity of AEs is recorded as mild, moderate, or severe.

A treatment-emergent adverse event (TEAE) is defined as an event that either first occurred or worsened in severity after the first dose of study treatment and on or prior to the last visit date during the analysis period. The analysis period is defined as the treatment period plus up to 30 days off-drug follow-up time.

Adverse events are classified based upon the MedDRA PT. The MedDRA Lowest Level Term (LLT) will be used in defining which events are treatment-emergent. The maximum severity for each LLT during the baseline period up to first dose of the study medication will be used as baseline. If an event with missing severity is pre-existing during the baseline period, and persists during the treatment period, then the baseline severity will be considered mild for determining treatment-emergence (that is, the event is treatment-emergent if the severity is coded moderate or severe postbaseline and not treatment-emergent if the severity is coded mild postbaseline). If an event occurring postbaseline has a missing severity rating, then the event is considered treatment-emergent unless the baseline rating is severe, in which case the event is not a treatment-emergent. The day and time for events where onset is on the day of the first dose of study treatment will both be used to distinguish between pretreatment and posttreatment to derive treatment-emergence. Should there be insufficient data for AE start date to make this comparison (for example, the AE start year is the same as the treatment start year, but the AE start month and day are missing), the AE will be considered treatment-emergent.

In general, summaries will include the number of patients in the safety population (N), frequency of patients experiencing the event (n), and relative frequency (that is, percentage;  $n/N*100$ ). For any events that are gender-specific based on the displayed PT, the denominator used to compute the percentage will only include patients from the given gender.

For selected safety topics, incidence rate (IR) per 100 patient-years of observation (PYR) will be provided for the Week 52, Week 104, and final analyses. See the Compound level safety standards for more details.

Adverse Events and Treatment Emergent AEs will be replicated based on the Safety Censoring rule 1 and 2.

Safety censoring rule 1 excludes the event if it's after the permanent study drug discontinuation, or dose change, whichever occurred earlier and Safety censoring rule 2 excludes the event if it's after the permanent study drug discontinuation.

Extended Safety Analysis includes patients who were continuously treated with Baricitinib 1mg, 2mg, or 4mg and Placebo from baseline and censored in case of dose change using Safety Censoring Rule 1. In addition to the above treatment groups “ALL BARI” will also be included to the summary which includes patients who received at least one dose (1 mg, 2mg, or 4mg) of BARICITINIB at any time of the treatment period.

In an overview table, the number and percentage of patients in the safety population who experienced death, an SAE, any TEAE, discontinuation from the study due to an AE, permanent

discontinuation from study drug due to an AE, TEAEs which are considered related to treatment by the investigator, or a severe TEAE will be summarized by treatment group.

The number and percentage of patients with TEAEs will be summarized by treatment group in 2 formats:

- by MedDRA PT nested within SOC with decreasing frequency in SOC, and events ordered within each SOC by decreasing frequency in the All baricitinib group
- by MedDRA PT with events ordered by decreasing frequency in the All baricitinib group.

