10.3.4. Safety Analyses

All safety data will be descriptively summarized by treatment groups and analyzed using the safety population, unless otherwise stated.

Treatment-emergent adverse events (TEAEs) are defined as AEs that first occurred or worsened in severity after the first dose of study treatment. The number of TEAEs as well as the number and percentage of patients who experienced at least 1 TEAE will be summarized using MedDRA (Medical Dictionary for Regulatory Activities) for each system organ class (or a body system) and each preferred term by treatment group. Serious adverse events and AEs that lead to discontinuation of investigational product will also be summarized by treatment group. Fisher exact test will be used to perform comparisons between each baricitinib dose and the placebo group. Further details will be provided in the SAP.

All clinical laboratory results will be descriptively summarized by treatment group. Individual results that are outside of normal reference ranges will be flagged in data listings. Quantitative clinical hematology, chemistry, and urinalysis variables obtained at the baseline to postbaseline visits will be summarized as changes from baseline by treatment group and analyzed using ANCOVA with treatment and baseline value in the model. Categorical variables, including the incidence of abnormal values and incidence of adverse events of interest, will be summarized by frequency and percentage of patients in corresponding categories. Shift tables will be presented for selected measures.

Observed values and changes from baseline (predose or screening if missing) for vital signs and physical characteristics will be descriptively summarized by treatment group and time point. Change from baseline to postbaseline in vital signs, and body weight will be analyzed using ANCOVA with treatment and baseline value in the model.

The incidence and average duration of investigational product interruptions will be summarized and compared descriptively among treatment groups. Various techniques may be used to estimate the effects of investigational product interruptions on safety measures. Further analyses may be performed and will be planned in the SAP.

Data collected after initiation of rescue therapy will be summarized as appropriate.

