The time period for safety analysis of the 24-week interim analysis will be following criteria whichever occurs first:

- up to last dose plus up to 30 days in the study
- the first dose in Period 3
- up to dose change or up to the data cutoff date

The time period for safety analysis of the 52-week interim analysis will be following criteria whichever occurs first:

- up to last dose plus up to 30 days in the study
- the study discontinuation date
- up to dose change
- the first dose date in Period 3

**The time period for safety analysis of the 104 interim analysis** will be following criteria whichever occurs first:

- up to last dose plus up to 30 days in the study
- the study discontinuation date
- up to dose change date due to rescue

- up to dose change date due to retreatment
- the first dose in Period 4
- up to the data cutoff date

**The time period for safety analysis of the final analysis** will be following criteria whichever occurs first:

- up to last dose plus 30 days or up to last date in the study
- the study discontinuation date
- up to dose change

**Long-Term Extension (LTE) Substudy Population:** The LTE Substudy Population is defined as the patients who received at least one study medication in Period 3 of Study JAIN, and entered the downtitration substudy. Additionally, those patients who did not met study discontinuation criteria in Period 3 and continued in Period 4 will be considered in the analysis set.

**Long-Term Extension(LTE) Substudy Relapse Population:** for a subset of patients in the LTE Substudy Population defined as above who experienced a relapse in Period 3 or Period 4 (IGA $\geq$ 3 after Week 52).

**Long-Term Extension(LTE) Non-responder Population:** The LTE Non-responder Population is defined as the patients who received at least one study medication in Period 3 of Study JAIN, and IGA $\geq$ 3 at Week 52. Additionally, those patients who did not met study discontinuation criteria in Period 3 and continued in Period 4 will be considered in the analysis set.

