#### *Period 3 and Period 4 (Study Weeks 52 to 200)*

For analysis of endpoints assessed at scheduled visits in Periods 3 and 4, baseline from Week 0 will be used for categorical endpoints, such as EASI75, Itch NRS  $\geq 4$ -point improvement response, etc. Baseline from Week 0 will also be used for EASI-related, continuous endpoints, such as EASI change or percent change from baseline. For the other continuous endpoints such as Itch NRS and Dermatology Life Quality Index (DLQI) change from baseline, the analysis will be done using the Week 52 baseline. The methodology for defining Week 52 as the baseline is the same as the methodology for defining Week 0 of the originating study described above, anchoring on the first study drug administration of Period 3. See [Table JAIN.6.9](#) and [Table JAIN.6.12](#) for a detailed descriptions on endpoint derivation and associated baseline definition.

Baseline daily-diary definition will be same to the Period 2's definition for daily-diary data.

Postbaseline measurements are collected after study drug administration through Week 200 (Visit 28) or early discontinuation visit. Data collected on scheduled visits will generally be used for efficacy and health outcome analyses. If data for a scheduled visit are missing, data from the most proximal unscheduled visits, if available, will be used if it falls within visit windows as follows: a 2-day interval around the scheduled visit day (4-day window) is applied to Visits 3 to 6 (Week 1, 2, 4, 8), a 4-day interval around the scheduled visit day (8-day window) is applied to Visits 7 to 9 (Week 12, 16, 20), a 5-day interval around the scheduled visit day (10-day window) is applied to Visits 10 to 14 (Week 24, 32, 40, 48, 52), a 4-day interval around the scheduled visit day (8-day window) is applied to Visits 15 to 18 (Week 56, 60, 64, 68), a 5-day interval around the scheduled visit day (10-day window) is applied to Visits 19 to 22 (Week 76, 84, 92, 104), and a 7-day interval around the scheduled visit day (14-day window) is applied to

Visits 23 to 28 (Week 120, 136, 152, 168, 184, and 200). If there is more than 1 unscheduled visit within the defined visit window and no scheduled visit is available, the unscheduled visit closest to the scheduled visit date will be used. If only 2 equal distance unscheduled visits are available, the later of the 2 visits will be used.

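### SAP 6.13.1 ends the treatment-emergent window at the last visit, in conflict with the 30-day window in SAP 6.13 and 6.2.1; followed literally, some known adverse events would not be flagged

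*SAP*

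**What the plan says.** SAP 6.13.1 defines a TEAE as an event that first occurred or worsened "after the first dose of study treatment and on or prior to the last visit date during the analysis period". Its next sentence reads: "The analysis period is defined as the treatment period plus up to 30 days off-drug follow-up time". The term last visit date is not defined, so it could mean a scheduled, unscheduled, early termination or follow-up visit.

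Other places set the end of follow-up differently:

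- Protocol 10.3.4 defines TEAEs as "AEs that first occurred or worsened in severity after the first dose of study treatment", with no upper limit in that sentence.
- SAP 6.13 says that for tables of events, AEs included, "post-last dose follow-up data will be included". It defines these data as "all data occurring up to 30 days (planned maximum follow-up time) after last dose of treatment including rescue". Patients who stopped drug before an interim lock "will be included in the interim lock safety analysis up to 30 days post last dose".
- SAP 6.2.1 sets the safety period for each lock as the earliest of several dates. For the final analysis the first of these is "up to last dose plus 30 days or up to last date in the study". The others, across the locks, are study discontinuation, dose change, first dose in the next period and data cutoff. None is a visit date.
- SAP 6.13.2 and 6.13.3 use the same treatment-plus-30-day period for categorical laboratory and vital-sign analyses, without a visit condition.

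**The concern.** The visit condition makes the TEAE window shorter than the analysis period that the same paragraph sets. Patients take drug between visits and are meant to be observed for up to 30 days after it. An event that is known to the site and falls inside that period, but is dated after the last visit the patient attended, fails the definition as written.

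At stake is the completeness of the displays that depend on the TEAE flag. Infections are a protocol AE of special interest, and their counts are among these displays.

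**Working it through.** The plan states no figure on this point, so there is none to reproduce. The check compares wording, does day arithmetic on the visit schedule, and gives one labelled illustration.

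**1. Which rule sets the flag.** SAP 6.13 says which data enter event tables. SAP 6.13.1 says which events count as treatment-emergent. A programmer who follows both would admit an event dated day 20 after last dose to the data, and still not flag it if the last attended visit was on the last day of dosing. The two sections therefore give different end dates for the same tables.

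**2. Days that can fall after the last visit but inside the period.**

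On drug, from the protocol's Schedule of Activities (longest nominal gap in weeks × 7):

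| Period | Longest gap | Days |
|---|---|---|
| 2 | for example Week 24 to 32 | 8 × 7 = 56 |
| 3 | Week 92 to 104 | 12 × 7 = 84 |
| 4 | for example Week 104 to 120 | 16 × 7 = 112 |

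Off drug, Visit 801 is due at 28 ± 4 days after last dose. Days of the 30-day window left after it = max(0, 30 − day of visit):

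- Visit on day 24: 30 − 24 = 6 days
- Visit on day 28: 30 − 28 = 2 days
- Visit on day 30 or later: 0 days
- No Visit 801 and no other visit after last dose: up to the full 30 days

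**3. Which displays depend on the flag.**

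- Dependent: the any-, related- and severe-TEAE overview rows and the SOC/PT tables (SAP 6.13.1); common TEAEs and maximum severity (6.13.1.1); TEAE infections, including treatment-emergent herpes zoster, tuberculosis and opportunistic infections (6.13.4.6).
- Not dependent: SAE tables and the death listing (6.13.1.2); drug or study discontinuation because of an AE (6.13.1 overview and 6.13.1.3); adjudicated MACE and VTE (6.13.4.7 and 6.13.4.8); malignancy summaries, which keep every case whatever the interval since last dose (6.13.4.10); registry SAEs (6.19).

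**4. Illustration of size.** The documents give no rate of patients without a closing visit. Assume 2% to 10% of an arm, of whom 10% to 30% have a known first event after the last visit. Patients missing from the any-TEAE row = N × share without a closing visit × share with such an event:

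- N = 100 (placebo, 1-mg, 4-mg): 100 × 0.02 × 0.10 = 0.2 to 100 × 0.10 × 0.30 = 3
- N = 200 (2-mg): 200 × 0.02 × 0.10 = 0.4 to 200 × 0.10 × 0.30 = 6

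**The case against.** The strongest reply is that this is a wording mismatch with little practical effect. Protocol 5.1.5 requires an early termination visit, and normally Visit 801, for patients who leave early, so most events will precede some visit. Patients lost to follow-up cannot be contacted (Protocol 8.3), so there is often no later event to record. Those lost at the first postbaseline visit are already outside the safety population. Events with insufficient start dates are treated as treatment-emergent. In the replicates under safety censoring rules 1 and 2, off-drug events drop out for a separate reason. Protocol 10.3.4 leaves detail to the SAP, and Protocol Appendix 1 ties TEAEs to a defined treatment period, so the protocol concept is not open-ended. Some derivation detail sits in the Compound level safety standards, which are not part of these documents.

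All of this stands as a limit on size. It does not remove the conflict. The censoring rules do not protect on-drug events after the last visit, and the data rule in SAP 6.13 does not change the flag.

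A reader might infer more than the documents support:

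- **That such events drop out of every TEAE table.** SAP 6.13 says follow-up data are included, so the SAP contradicts itself and exclusion is not settled.
- **That the events most likely to end participation disappear from the report.** Deaths, SAEs and AE-related discontinuations are tabulated without TEAE status.
- **That malignancies are lost.** SAP 6.13.4.10 says otherwise.
- **That incidence rates are understated because exposure continues to last dose.** SAP 6.13.1 bases incidence rates on patient-years of observation, for selected topics only, and the general AE summaries are percentages of patients.

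**Conclusion.** SAP 6.13.1 states a TEAE end date that is narrower than its own analysis period, differs from SAP 6.13 and 6.2.1, and does not appear in Protocol 10.3.4. Read literally, it leaves unflagged any known AE that is on drug or within 30 days of last dose but dated after the last attended visit. The patients concerned are mainly those who die between visits, stop attending or miss Visit 801. Up to 6 days of the window are also lost when Visit 801 falls on day 24.

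The size cannot be found from the documents. It is probably small: the 0.2 to 3 patients per 100 rests entirely on the assumed shares above. The rule applies to all arms, and nothing in the documents shows a differential effect. The primary and key secondary efficacy results are unaffected. The point should be corrected because the rule, as written, can only lower TEAE and treatment-emergent infection counts, and the SAP gives no reason for it.

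**What to change.** In SAP 6.13.1, replace the visit condition at the end of the TEAE definition with: *on or before the end of the analysis period, that is, the earliest of last dose + 30 days, last date in the study (including date of death), and the analysis cut in Section 6.2.1*. The TEAE flag then agrees with SAP 6.13 and 6.2.1. If the sponsor wants to keep a visit-based limit, the SAP should define last visit date and justify the restriction.

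The cost is one sentence and one date variable in the TEAE derivation. TEAE counts may rise slightly.
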